APPENDIX III The Charlson's comorbidity index (CCI)

CCI is defined after adding the score for age to the score for co-morbidities.

The score for age is given below:

Age group (years)	Points
0-49	0
50-59	1
60-69	2
70-79	3
80-89	4
90-99	5

The score for comorbidities is given below:

Condition	Points
None	0

 Myocardial infarct (one or more definite or probable myocardial infarctions)	1

 Congestive heart failure (exertional or paroxysmal nocturnal dyspnea treated with digitalis, diuretics, or afterload reducing agents)	

 Peripheral vascular disease (intermittent claudication or bypass for arterial insufficiency or gangrene or acute arterial insufficiency or an untreated thoracic or abdominal aneurysm ≥ 6 cm)	

 Cerebrovascular disease (except hemiplegia) (history of a cerebrovascular accident with minor or no residua and transient ischemic attacks)	

 Dementia (defined as chronic cognitive deficit) 	

 Chronic pulmonary disease 	

- Connective tissue disease

(systemic lupus erythematosus, polymyositis, mixed connective tissue disease, polymyalgia rheumatic and moderate to severe rheumatoid arthritis)

- Peptic ulcer disease
- Mild liver disease (cirrhosis without portal hypertension or chronic hepatitis)
- Diabetes (without complications)

-
- Diabetes with end organ damage 2

(Retinopathy, neuropathy, nephropathy, previous hospitalizations for ketoacidosis, hyperosmolar coma, or juvenile onset or brittle diabetics)

- Hemiplegia
- Moderate or severe renal disease

(moderate defined as serum creatinine of 2-3 mg/dl, severe defined as need for dialysis/transplantation)

- Solid tumor (non-metastatic)

(without documented metastases, but initially treated in the last five years)

- Leukemia/lymphoma/multiple myeloma

-
- Moderate or severe liver disease 3

(Moderate: cirrhosis with portal hypertension; severe: cirrhosis with portal hypertension and a history of variceal bleeding)

-
- Metastatic solid tumor 6
 - AIDS (acquired immunodeficiency syndrome) (Definite or probable AIDS)
-

APPENDIX IV Study visits

Visit	Screening	1	2	3	4	5
Day		0	45 ± 5	90 ± 5	135 ± 5	180 ± 5
Informed consent	x					
Exclusion criteria	x					
Inclusion criteria	x					
IgG/IgM	x			x		
PPD	x					
Comorbidities	x	x				
Recent hospitalizations		x				
Vaccination		x				
Questionnaire		x	x	x	x	x
Cardiovascular events		x	x	x	x	x
Blood sampling*		x		x		x
Vascular ultrasound*		x		x		x
Heart ultrasound*		x		x		x

*only for participants in the sub-study

APPENDIX VI Questionnaire addressed to patients on study visits

The questionnaire is composed of questions referring to symptoms possible related to COVID-19, probably related to COVID-19 and definitively related to COVID-19.

Did you present any of the following symptoms during the last 45 days (please answer with YES or NO to any of the following infections):	YES	NO
Symptoms possibly related to COVID-19		
• Cough for more than 48 hours without any other symptoms		
• Shortness of breath for more than 48 hours without any other symptoms		
• Fever above >38°C for more than 48 hours without any other symptoms		
• Expectoration for more than 48 hours without any other symptoms		
Symptoms probably related to COVID-19		
• Cough and shortness of breath for more than 48 hours		
• Cough and fever for more than 48 hours		
• Fever and shortness of breath for more than 48 hours		
• Fever and expectoration for more than 48 hours		
• Need for admission at the emergency department of any hospital		
• Need for intake of antibiotics		
Situation definitively related to COVID-19		
• Had known diagnosis of COVID-19 by molecular test		

Patients score positive for the respiratory questionnaire endpoint if they have one of the following combination:

- One situation definitively related to COVID-19
- All four questions of symptoms possibly related to COVID-19 answered YES

- At least two questions of symptoms possibly related to COVID-19 answered YES + need for admission at the emergency department of any hospital and/or need for intake of antibiotics answered YES
- At least four questions of symptoms probably related to COVID-19 answered YES one of which is “need for admission at the emergency department of any hospital and/or need for intake of antibiotics”

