- For patients who continue screening process, a diagnostic test using blood from the fingertip to detect IgG/IgM antibodies against the SARS-CoV-2 virus takes place (inclusion criterion 6). If the test is positive for any of IgM or IgG antibodies, screening stops. If the test for both IgG / IgM antibodies is negative, the patient may be included in the trial.

Sub-Study

Participants who will be included in the study in the Department of Clinical Therapeutics of the ALEXANDRA General Hospital of Athens, will participate in a sub-study at the Vascular Laboratory of the Therapeutic Clinic. The sub-study procedures are carried out within the framework of the planned visits of the patients and are analyzed in the paragraph "Patient visits and interventions".

Study visits (APPENDIX IV)

Visit 1 This visit is conducted immediately after the end of the screening procedure (month 0 of study) and involves the following:

- Recording of the following information: age and gender, pre-existing comorbidities, history of hospitalizations the last two years
- For the participants of the sub-study, the following procedures will be performed:
 - a) carotid and femoral artery ultrasound, b) heart ultrasound, and c) a blood sample of 10 ml (peripheral blood) will be collected for PBMC stimulation for cytokine production (see section "Sub-study procedures")
- Administration of placebo or BCG

Visit 2 This visit is conducted 45 ± 5 days from the date of visit 1. This visit may be done by phone call or through the internet. During this visit, the vaccinated subject is asked to provide answers to a specific questionnaire involving the incidence of respiratory tract infection (Appendix VI). All patients will also be asked for the incidence of cardiovascular events, such as any diagnosis of stroke, myocardial infarction or rupture of a abdominal aortic aneurysm.

Visit 3 This visit is conducted 90 ± 5 days from the date of visit 1. This is a visit conducted at the study site. During this visit, the following are done:

- IgG and IgM antibodies against SARS-CoV-2 are measured in the vaccinated subject in exactly the same method that was followed at the screening stage
- The vaccinated subject is asked to provide answers to a specific questionnaire involving the incidence of respiratory tract infection (Appendix VI). All patients will

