be asked for the incidence of cardiovascular events, such as any diagnosis of stroke, myocardial infarction or rupture of a abdominal aortic aneurysm.

- For the participants of the sub-study, the following procedures will be performed:
 - a) carotid and femoral artery ultrasound, b) heart ultrasound, and c) a blood sample of 10 ml (peripheral blood) will be collected for PBMC stimulation for cytokine production (see section "Sub-study procedures")

Visit 4 This visit is conducted 135 ± 5 days from the date of visit 1. This visit may be done by phone call or through the internet. During this visit, the vaccinated subject is asked to provide answers to a specific questionnaire involving the incidence of respiratory tract infection (Appendix VI). All patients will be asked for the incidence of cardiovascular events, such as any diagnosis of stroke, myocardial infarction or rupture of a abdominal aortic aneurysm.

Visit 5 This visit is conducted 180 ± 5 days from the date of visit 1. This visit may be done by phone call or through the internet. During this visit, the vaccinated subject is asked to provide answers to a specific questionnaire involving the incidence of respiratory tract infection (Appendix VI). All patients will be asked for the occurrence of cardiovascular events, such as any diagnosis of stroke, myocardial infarction or rupture of a abdominal aortic aneurysm. For the participants of the sub-study, the following procedures will be performed: a) carotid and femoral artery ultrasound, b) heart ultrasound, and c) a blood sample of 10 ml (peripheral blood) will be collected for PBMC stimulation for cytokine production (see section "Sub-study procedures")

It is explicitly stated that the investigators will encourage vaccinated population to refer to them in case of the incidence of any infection-related symptom.

PROCEDURES OF THE SUB-STUDY

Vaccinated people should abstain from food, alcohol and caffeine, smoking, and vasodilators for 12 hours before performing angiographic imaging studies. The exams to be taken are as follows:

- Arterial stiffness in the aorta from the speed of the pulse wave: It will be evaluated using a special non-invasive device (Complior, Artech Medical, France) in a non-bloody way on the carotid arteries and femoral arteries.

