- Central blood pressure and reflected aortic waves: It will be evaluated using a special automated device (SphygmoCor System, AtCor Medical Pty Ltd, Sydney, Australia) in a non-bloody way on the carotid and femoral arteries.
- Endothelial function with ultrasound measurement of the dependent-from-the-endothelial dilation and mediated-from-the-nitrite dimension: It will be assessed using an ultrasound device and the measurement of the route-dependent vasodilator using a special 7-14 MHz audio recorder (Vivid 7 Pro, GE, USA) to be applied in a non-bloody way to the carotid and femoral arteries
- Carotid arteries intima-media thickness and Uterine Arteries: It will be evaluated using a B-mode ultrasound device and a special sound system (14.0 MHz multi-frequency linear array probe, Vivid 7 Pro, GE Healthcare, USA) in a non-bloody way on the carotid arteries. and femoral arteries.
- Cardiac ultrasound: The standard procedures of the clinical practice will be followed and the standard measurements will be taken using 2-D and Doppler ultrasound techniques.
- One blood sample will be taken from a forearm vein after antiseptic application and will be collected in tubes with anticoagulant agent. Isolation of PBMCs will be performed and they will be stimulated with purified bacterial antigens for cytokine production.

STUDY ENDPOINTS

Primary endpoint

The primary study endpoint is set on visit 3 (90 ± 5 days from the date of visit 1). The two groups of vaccination are compared for the primary endpoints which is composite. Patients who meet any of the following will be considered to meet the primary endpoint:

- Positive for the respiratory questionnaire endpoint when at least one of the following combination is met either at visit 2 and/or at visit 3 (see APPENDIX VI):
 - One situation definitively related to COVID-19

- All four questions of symptoms possibly related to COVID-19 answered YES
- At least two questions of symptoms possibly related to COVID-19 answered YES + need for admission at the emergency department of any hospital and/or need for intake of antibiotics answered YES
- At least four questions of symptoms probably related to COVID-19 answered YES one of which is “need for admission at the emergency department of any hospital and/or need for intake of antibiotics”
- Positive IgG or IgM antibodies against SARS-CoV-2

Secondary endpoints

The secondary endpoints are the difference between the two groups of vaccination in each of the following:

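### The questionnaire's fixed 45-day recall does not match visits that may move by ±5 days, so it does not reliably cover the post-injection window of the primary endpoint

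*Protocol*

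**What the plan says.** The stem of the questionnaire in Protocol Appendix VI is "Did you present any of the following symptoms during the last 45 days". The same form is used at every questionnaire visit. Answers are YES or NO, and the form has no field for an onset date.

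The injection is given at visit 1 ("Administration of placebo or BCG"), which Appendix IV labels day 0. For visit 2 the Study visits section says "This visit is conducted 45 ± 5 days from the date of visit 1" and "This visit may be done by phone call or through the internet". Visit 3, where the primary endpoint is set, is at 90 ± 5 days.

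Under Study endpoints, the questionnaire part of the composite is positive when "at least one of the following combination is met either at visit 2 and/or at visit 3". The other part is serology at visit 3: "IgG and IgM antibodies against SARS-CoV-2 are measured in the vaccinated subject".

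Two further provisions bear on the point:

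- Between visits, "investigators will encourage vaccinated population to refer to them in case of the incidence of any infection-related symptom". The protocol does not say that such reports count towards the endpoint.
- The Appendix IV schedule marks a questionnaire at visit 1, but the visit 1 procedures in the text do not list one, and no rule says how its answers would be used.

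**The concern.** A recall equal to the nominal visit interval covers the whole period only if no interval exceeds 45 days. The visit windows allow visits 2 and 3 to be 55 days apart and visit 2 to be 50 days after injection. They also allow visit 2 to come before day 45, when a 45-day recall reaches back past the injection.

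The endpoint is meant to describe what happens in the three months after vaccination. If the form is used as printed, some days of that period are not asked about, and some earlier days may be. If the visit 2 contact does not happen, the visit 3 form still reaches back only 45 days.

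This is a matter of what is collected, not of analysis. Without onset dates, a statistical analysis plan can neither recover an episode that was never asked about nor remove one that began before injection.

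**Working it through.** **Inputs.** Recall: 45 days ending on the contact day (Appendix VI). Visit 2: day d2 from 40 to 50. Visit 3: day d3 from 85 to 95 (Study visits; Appendix IV). Injection: day 0. Post-injection days are counted from day 1.

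**Formulas.**

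- Unasked days = max(0, d2 − 45) + max(0, d3 − d2 − 45)
- Pre-injection days asked about = max(0, 45 − d2)
- Unasked days if visit 2 is missed = d3 − 45

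**Single cases.**

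| Visit 2 | Visit 3 | Unasked days | Pre-injection days asked about |
|---|---|---|---|
| 45 | 90 | 0 | 0 |
| 40 | 85 | 0 | 5 |
| 40 | 95 | 0 + 10 = 10 (days 41–50) | 5 |
| 45 | 95 | 0 + 5 = 5 (days 46–50) | 0 |
| 50 | 90 | 5 + 0 = 5 (days 1–5) | 0 |
| missed | 85 | 40 of 85 (47%) | – |
| missed | 90 | 45 of 90 (50%) | – |
| missed | 95 | 50 of 95 (53%) | – |

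**All permitted pairs.** There are 11 × 11 = 121. Of these, 100 (83%) leave at least one day unasked. The gaps sum to 385 days, so the mean is 385/121 = 3.2 days and the maximum is 10. In 55 pairs (45%) the visit 2 form reaches before injection, by at most 5 days.

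The mean weights all pairs equally, which is an assumption. Repeating the count with a narrower spread of actual visit days gives:

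| Spread around days 45 and 90 | Pairs with a gap | Mean gap |
|---|---|---|
| exact | 0 of 1 | 0 |
| ±1 day | 6 of 9 (67%) | 7/9 = 0.8 day |
| ±2 days | 19 of 25 (76%) | 35/25 = 1.4 days |
| ±5 days | 100 of 121 (83%) | 3.2 days |

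**Effect on power.** The plan's own figure comes first. For 20.4% against 12.2%, 90% power and two-sided 5% (the protocol does not state sidedness), the normal approximation gives 425 per group without continuity correction and 449 with it. The stated 437 lies between them and is not in dispute.

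Power at n = 437 is Φ{[δ − 1.96·√(2p̄(1 − p̄)/n)] / √((p1q1 + p2q2)/n)}, where q = 1 − p. With δ = 0.082 and p̄ = 0.163:

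- 1.96·√(0.2729/437) = 0.0490
- √(0.2695/437) = 0.0248
- (0.0820 − 0.0490)/0.0248 ≈ 1.33, so power is 90.8%

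Now assume that events are spread evenly over the window and are found only by questionnaire, and multiply both rates by (1 − f), where f is the share of days lost. If a proportion m misses visit 2, f = m × 0.5.

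| Loss | f | Power at 437 per group |
|---|---|---|
| none | 0 | 90.8% |
| mean gap, 3.2 of 90 days | 0.035 | 89.6% |
| 5 of 90 days for everyone | 0.056 | 88.9% |
| 10 of 95 days for everyone | 0.105 | 86.8% |
| 5% miss visit 2 | 0.025 | 90.0% |
| 10% miss visit 2 | 0.050 | 89.1% |
| 20% miss visit 2 | 0.100 | 87.1% |

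The protocol gives no missed-contact rate, so the last three rows show a range and are not estimates.

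**The case against.** The case for leaving the form alone is that the consequences are small and partly covered elsewhere.

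- **Serology does not depend on recall.** The IgG/IgM test at visit 3 can detect a SARS-CoV-2 infection from unasked days. This stands, and it limits the loss of confirmed COVID-19 cases: the form may miss a molecular diagnosis that the antibody test then picks up. It does not help with the symptom, emergency-department and antibiotic combinations.
- **Day counts look more exact than recall is.** The symptom items require more than 48 hours, so an episode running past a short gap can still be reported, and nobody remembers to the exact forty-fifth day. This stands as a reason not to read much into one or two days. It does not answer a ten-day gap or a missed visit 2.
- **The 83% overstates the harm.** This also stands. It counts any pair with a single unasked day, so it is not a forecast that 83% of participants will have a gap. At ±1 day the share is still 67%, although the mean gap is only 0.8 day.
- **A visit 1 questionnaire would record illness before injection.** This stands only in part, because the schedule and the visit 1 text disagree and no rule uses such a record to exclude earlier illness.
- **Participants are encouraged to report symptoms between visits.** They are, but those reports are not linked to endpoint scoring.

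A reader might also infer that a participant who misses visit 2 is scored negative. The protocol says when a participant is positive. It does not say how one with no visit 2 questionnaire is classified, and that may properly sit in a statistical analysis plan not shown here.

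**Conclusion.** The mismatch is real and follows from the protocol's own figures. Within the permitted windows, up to 10 post-injection days are unasked and up to 5 pre-injection days are asked about. If visit 2 is missed, 47–53% of the period is covered by no questionnaire. Coverage is complete when visits fall exactly on days 45 and 90.

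The size is modest. The illustrations put the loss of power at roughly 1 to 4 points, assuming evenly spread events that only the questionnaire can find. Because serology is a second route, these figures are more likely too high than too low.

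A reader might go further and infer bias between the arms, or suppose that ill participants are the ones who miss the visit 2 call or attend visit 3 late. The documents support neither. Both arms use the same form and windows, the stated aim is a double-blind comparison, and nothing is said about who misses contacts. What can be said is that events will be lost or misdated, and that the missing days cannot be recovered once the form has been used. For a primary endpoint, and at so small a cost, the wording should be changed.

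**What to change.** In Appendix VI, replace the fixed 45-day stem with a dated one:

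- Visit 2: *since your injection on [date]*
- Visits 3, 4 and 5: *since your last completed study questionnaire on [date], or since your injection if none*

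For every permitted pair of visits 2 and 3 this gives zero unasked days and zero pre-injection days. After a missed visit 2, the visit 3 form would cover all 85–95 days instead of 45. The sample size does not change.

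The cost is one line of the form with a pre-filled date, and nothing changes when visits are on time. The downside is longer, slightly less accurate recall after a late or missed contact, which is still better than not asking.

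The visit 1 text and the Appendix IV schedule should also be brought into agreement on whether a questionnaire is completed on day 0.

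### Primary-endpoint questionnaire: the four 'possible' items each exclude other symptoms, yet two scoring rules need several of them, so one concurrent illness cannot meet either rule

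*Protocol*

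**What the plan says.** The primary endpoint (protocol synopsis; Study Endpoints, Primary endpoint) is a composite at visit 3. It is met by a positive respiratory questionnaire at visit 2 and/or visit 3, or by positive IgG or IgM against SARS-CoV-2. The questionnaire and its scoring are in Appendix VI.

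- **Possible items (four).** Cough, shortness of breath, fever and expectoration, each lasting more than 48 hours and each as a sole symptom: "Cough for more than 48 hours without any other symptoms"; "Fever above >38°C for more than 48 hours without any other symptoms".
- **Probable items (six rows).** Four symptom pairs (cough with shortness of breath; cough with fever, worded "Cough and fever for more than 48 hours"; fever with shortness of breath; fever with expectoration), then "Need for admission at the emergency department of any hospital" and "Need for intake of antibiotics" on separate rows.
- **Definitive item.** A known molecular diagnosis.

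Any one of four rules makes the questionnaire positive:

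1. The definitive item.
2. "All four questions of symptoms possibly related to COVID-19 answered YES".
3. At least two possible items plus ED admission and/or antibiotics.
4. "At least four questions of symptoms probably related to COVID-19 answered YES one of which is" the ED and/or antibiotics question, which the rule quotes as a single question.

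The recall question is "Did you present any of the following symptoms during the last 45 days". Visits 2 and 3 are on days 45 ± 5 and 90 ± 5.

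**The concern.** The items and the rules contradict each other. An illness with two symptoms at once earns no YES on the possible items, because each demands the absence of any other symptom. An illness with one isolated symptom earns one. Yet rule 2 needs four and rule 3 needs two.

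This is the clinical half of a binary primary endpoint that is compared by Fisher's exact test. The sample size takes its event rates from total respiratory infections in the earlier ACTIVATE trial. Appendix I describes those as respiratory or viral infections needing medical treatment and pneumonias. If the form rejects many illnesses of that kind, the planning rates may not apply. The wording decides what participants are asked, so an answer that was never collected cannot be recovered at analysis.

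**Working it through.** **The plan's own figure.** Inputs from Study Power Calculation: 20.4% against 12.2%, 5% significance, 90% power, 437 per group. The two-sided formula is

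n = [1.960·√(2·p̄(1−p̄)) + 1.282·√(p₁(1−p₁) + p₂(1−p₂))]² / (p₁−p₂)²,

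with p₁ = 0.204, p₂ = 0.122 and p̄ = 0.163. It gives 425 per group, or 449 with continuity correction. The stated 437 lies within 3% of both and is not in dispute. Exact power of Fisher's test at 437 per group is 0.896.

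**The example.** One illness with concurrent cough and fever, ED admission YES, antibiotics YES, no molecular diagnosis:

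| Rule | Needed | Obtained | Met? |
|---|---|---|---|
| 1 | molecular diagnosis | none | no |
| 2 | 4 possible items | 0 | no |
| 3 | 2 possible items plus care | 0 | no |
| 4 | 4 probable items | 1 pair + 2 = 3 (ED and antibiotics separate) or 1 + 1 = 2 (merged) | no |

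The result is negative under either count.

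**All single-illness presentations.** Symptom sets with at least two of the four symptoms: 6 + 4 + 1 = 11. Care patterns with ED and/or antibiotics: 3. Total 11 × 3 = 33. Possible items are zero throughout, so only rule 4 can operate when there is no molecular diagnosis.

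| Symptoms | Pairs | Positive, separate count | Positive, merged count |
|---|---|---|---|
| Cough, breathlessness, fever | 3 | 3 of 3 | 3 of 3 |
| All four | 4 | 3 of 3 | 3 of 3 |
| Cough, fever, expectoration | 2 | 1 of 3 (both ED and antibiotics) | 0 of 3 |
| Breathlessness, fever, expectoration | 2 | 1 of 3 (both ED and antibiotics) | 0 of 3 |
| The other seven sets | 0 or 1 | 0 of 21 | 0 of 21 |
| **Total** | | **8 of 33** | **6 of 33** |

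The fever-free sets number 4, giving 4 × 3 = 12 presentations. None is positive: the only fever-free pair is cough with breathlessness, so the most they reach is 1 + 2 = 3. The item count changes the result in 8 − 6 = 2 presentations. With the sole-symptom condition removed, every set has at least two possible items plus care, and all 33 are positive by rule 3.

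**Power, as illustration only.** Assume the endpoint captures a fraction s of the planned events equally in both arms, with 437 per group and exact Fisher power:

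| s | Rates | Power |
|---|---|---|
| 1 | 20.4% v 12.2% | 0.896 |
| 0.8 | 16.3% v 9.8% | 0.80 |
| 0.5 | 10.2% v 6.1% | 0.56 |
| 0.25 | 5.1% v 3.05% | 0.28 |

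No value of s follows from the documents, and s is not 8/33.

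**Recall window.** On nominal dates (days 45 and 90) nothing is missed. In the worst case visit 2 is on day 40 and visit 3 on day 95. Visit 3 then looks back to day 95 − 45 = 50, so days 40 to 50 (10 days) are not asked about. A day-40 visit 2 looks back to day 40 − 45 = −5, five days before vaccination.

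**The case against.** Several stronger readings are tempting, and the documents do not support them.

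- *Rules 2 and 3 can never be met.* They can. Over 45 days, separate or successive isolated-symptom episodes of more than 48 hours could give two or four YES answers. The rules then detect sequences of isolated symptoms and not a combined illness.
- *The unclear item count causes the cough-and-fever example.* It does not: the score is 3 or 2, both below 4. Counting rows is also the natural reading of the form. The ambiguity is a separate, smaller defect.
- *Such a participant fails the primary endpoint.* Not necessarily. A molecular diagnosis is sufficient on its own, and so is positive IgG or IgM at visit 3.
- *The form captures about a quarter of illnesses, so the trial cannot answer its question.* The 33 presentations are unweighted combinations, not patients, and serology and molecular diagnosis add events outside the symptom rules. The fall in event rate is a risk and has not been shown.
- *The recall gap is serious.* It is zero on nominal dates, and the same schedule applies to both arms. Appendix IV also schedules the questionnaire at visit 1, so symptoms before vaccination may be on record.

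It can also be said that participants will not answer so literally. That does not help: endpoint status would then depend on how each respondent treats the condition.

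The objections limit the size of the claim. They do not reconcile the sole-symptom items with rules 2 and 3.

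**Conclusion.** The questionnaire is wrong as written and should be corrected. One concurrent illness cannot meet two of the three symptom-based rules. Without a molecular diagnosis it can score only through four probable items, which 8 of 33 multi-symptom presentations with medical care reach (6 under the merged count), and none of the 12 fever-free ones. This assumes one illness with concurrent symptoms and answers that follow the printed wording.

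The planning rates of 20.4% and 12.2% may not carry over to this endpoint. How far they fail to do so cannot be computed from the protocol; power of about 0.56 or 0.28 follows only if one half or one quarter of events is captured in both arms.

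Two secondary points remain: the ED and antibiotics count, which decides 2 of the 33 presentations, and the fixed recall period, which leaves at most 10 days unasked.

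**What to change.** Amend Appendix VI and carry the same text into the synopsis and the endpoint section:

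1. Remove the sole-symptom condition from the four possible items, so that each symptom is recorded whether or not others are present.
2. Keep the symptom pairs as questions on the form, worded as occurring together. Do not derive them from the single-symptom answers: cough in one week and fever several weeks later would otherwise become a combination.
3. State that ED admission and antibiotics count as two questions, as the form lists them.
4. Restate the scoring rules so that the intended tiers are explicit. After step 1, rule 3 absorbs rule 4: four probable items with at most two from care require at least two pairs, hence at least two symptoms plus care.
5. Replace the fixed 45-day recall with the time since vaccination (visit 2) or since the last study contact (later visits).

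The cost is a protocol amendment and a revised one-page form, with no added visit. The drawback is that more respiratory illness not due to COVID-19 will be counted, which may dilute the contrast between the arms. The restated tiers should be chosen with that in mind.
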